5.5.2 Definition of Serious Adverse Events (SAEs)

An AE is considered "serious" if, in the view of either the Investigator or Sponsor, it results in any of the following outcomes:

- Results in death
- Is life threatening (an AE is considered "life-threatening" if, in the view of either the Investigator or Sponsor, its occurrence places the subject at immediate risk of death. It does not include an AE that, had it occurred in a more severe form, might have caused death)
- Results in persistent or significant disability/incapacity or substantial disruption of the ability to conduct normal life functions
- Results in congenital anomaly, or birth defect
- Requires inpatient hospitalization or leads to prolongation of hospitalization (hospitalization for treatment/observation/examination caused by AE is to be considered as serious)
- Other medically important events

Medical and scientific judgment should be exercised in deciding whether expedited reporting is appropriate in other situations, such as important medical events that may not be immediately life-threatening or result in death or hospitalization but may jeopardize the subject or may require intervention to prevent one of the other outcomes listed in the definition above. These events, including those that may result in disability/incapacity, should also usually be considered serious. Examples of such events are intensive treatment in an emergency room or at home for allergic bronchospasm; blood dyscrasias or convulsions that do not result in hospitalization; or development of drug dependency or drug abuse.

Safety events of interest on the medicinal products administered to the subject as part of the study (e.g., study drug, comparator, background therapy) that may require expedited reporting and/or safety evaluation include, but are not limited to:

- Overdose of the study drug(s)
- Suspected abuse/misuse of the study drug(s)
- Inadvertent or accidental exposure to the study drug(s)
- Medication error involving the study drug(s) (with or without subject/patient exposure to the Sponsor medicinal product, e.g., name confusion)

All of the events of interest noted above should be documented within the source. Any situation involving these events of interest that also meets the criteria for an SAE should be handled as described in Section 5.5.5 Reporting of Serious Adverse Events.

The Sponsor has a list of events that they classify as “always serious” events. If an AE is reported that is considered to be an event per this classification as “always serious”, additional information on the event may be requested.

5.5.3 Criteria for Causal Relationship to the Study Drug

Adverse events that fall under either "Possible" or "Probable" should be defined as "AEs whose relationship to the study drugs could not be ruled out".

Causal relationship to the study drug	Criteria for causal relationship
Not related	A clinical event, including laboratory test abnormality, with a temporal relationship to drug administration which makes a causal relationship improbable, and/or in which other drugs, chemicals or underlying disease provide plausible explanations.
Possible	A clinical event, including laboratory test abnormality, with a reasonable time sequence to administration of the drug, but which could also be explained by concurrent disease or other drugs or chemicals. Information on drug withdrawal may be lacking or unclear.
Probable	A clinical event, including laboratory test abnormality, with a reasonable time sequence to administration of the drug, unlikely to be attributed to concurrent disease or other drugs or chemicals, and which follows a clinically reasonable response on readministration (rechallenge) or withdrawal (dechallenge).

5.5.4 Criteria for Defining the Severity of an Adverse Event

AEs, including abnormal clinical laboratory values, will be graded using the NCI CTCAE guidelines (Version 4.03). The items that are not stipulated in the NCI CTCAE Version 4.03 will be assessed according to the criteria below and will be documented within the source:

Grade	Assessment Standard
1-Mild	Asymptomatic, or mild symptoms, clinical or diagnostic observations noted; intervention not indicated.
2-Moderate	Local or noninvasive intervention indicated.
3-Severe	Medically significant but not immediately life-threatening, hospitalization or prolonged hospitalization.
4-Life-threatening	Life-threatening consequences, urgent intervention indicated
5-Death	Death related to AE

5.5.5 Reporting of Serious Adverse Events (SAEs)

In the case of a SAE, which will be collected from signing of the ICF until 30 days after last study drug administration, the Investigator must contact the Sponsor by telephone, fax or email immediately (within 24 hours of awareness).

The Investigator should complete and submit an SAE Worksheet containing all information that is required by the regulatory authorities to the Sponsor by fax or email immediately (within 24 hours of awareness). If the faxing or emailing of an SAE Worksheet is not possible or is not possible within 24 hours, the local drug safety contact shown in Section II Contact Details of Key Sponsor's Personnel should be informed by telephone.

For contact details, see Section II Contact Details of Key Sponsor's Personnel. Please fax or email the SAE Worksheet to:

Astellas Pharma Global Development – United States
Pharmacovigilance
[contact]
Email: [contact]

If there are any questions, or if clarification is needed regarding the SAE, please contact the Sponsor's Medical Monitor/Expert or his/her designee (see Section II Contact Details of Key Sponsor's Personnel).

Follow-up information for the event should be sent promptly (within 7 days of the initial notification).

Full details of the SAE should be recorded on the medical records and on the electronic case report form (eCRF).

The following minimum information is required:

- International Study Number (ISN)/Clinical Study Number,
- Subject number, sex and age,
- The date of report,
- A description of the SAE (event, seriousness of the event), and
- Causal relationship to the study drug.

The Sponsor or Sponsor's designee will submit expedited safety reports (i.e., Investigational New Drug [IND] Safety Reports) to the regulatory agencies (i.e., FDA) as necessary, and will

inform the Investigators of such regulatory reports. Investigators must submit safety reports as required by their IRB/IEC within timelines set by regional regulations (i.e., EU, eCTD, FDA). Documentation of the submission to and receipt by the IRB/IEC of expedited safety reports should be retained by the site.

The Sponsor will notify all Investigators responsible for ongoing clinical studies with the study drug of all SAEs which require submission per local requirements (IRB/IEC / head of the study site).

The Investigators should provide written documentation of IRB/IEC notification for each report to the Sponsor.

The Investigator may contact the Sponsor's Medical Monitor/Expert for any other problem related to the safety, welfare or rights of the subject.

For SUSAR from a blinded trial, unblinded Council for International Organizations of Medical Sciences (CIOMS)-I report will be submitted to the authorities and IEC where required.

5.5.6 Follow-up of Adverse Events

All AEs occurring during or after the subject has discontinued the study are to be followed up until resolved or judged to be no longer clinically significant, or until they become chronic to the extent that they can be fully characterized.

If during AE follow-up, the AE progresses to an "SAE", or if a subject experiences a new SAE, the Investigator must immediately report the information to the Sponsor.

5.5.7 Monitoring of Common Serious Adverse Events

Common SAEs are SAEs commonly anticipated to occur in the study population independent of drug exposure. SAEs classified as "common" are provided in Appendix 12.2 Common Serious Adverse Events. The list does NOT change the Investigator's reporting obligations or prevent the need to report an AE meeting the definition of an SAE as detailed above. The purpose of this list is to alert the Investigator that some events reported as SAEs may not require expedited reporting to the regulatory authorities based on the classification of "common SAEs" as specified in Appendix 12.2 Common Serious Adverse Events. The Sponsor will monitor these events throughout the course of the study for any change in frequency. Any changes to this list will be communicated to the participating investigational sites. Investigators must report individual occurrences of these events as stated in Section 5.5.5 Reporting of Serious Adverse Events.

5.5.8 Procedure in Case of Pregnancy

If a female subject or partner of a male subject becomes pregnant during treatment, this should be reported as if it was an SAE (refer to Section 5.5.8 Procedure in Case of Pregnancy). Administration of study drug must be discontinued in case evidence of pregnancy is obtained during the treatment period. The expected date of delivery or expected date of the end of the pregnancy, last menstruation, estimated conception date, pregnancy

result and neonatal data etc., should be included in this information. Should the partner of the male subject become pregnant, a separate ICF will be submitted for IRB/IEC review and approval that, upon signing by the pregnant female, will allow medical supervision during the pregnancy and allow follow-up after the birth of the infant.

The Investigator will follow the medical status of the mother, as well as the fetus, as if the pregnancy is an SAE and will report the outcome to the Sponsor.

When the outcome of the pregnancy falls under the criteria for SAEs [spontaneous abortion, induced abortion, stillbirth, death of newborn, congenital anomaly (including anomaly in a miscarried fetus)], the Investigator should respond in accordance with the report procedure for SAEs. Additional information regarding the outcome of a pregnancy (which is categorized as an SAE) is mentioned below.

- "Spontaneous abortion" includes miscarriage, abortion and missed abortion
- Death of an infant within 1 month after birth should be reported as an SAE regardless of its relationship with the study drug
- If an infant dies more than 1 month after the birth, it should be reported if a relationship between the death and intrauterine exposure to the study drug is judged as "possible" by the Investigator
- In the case of a delivery of a living newborn, the "normality" of the infant is evaluated at the birth
- Unless a congenital anomaly are identified prior to spontaneous abortion or miscarriage, the embryo or fetus should be assessed for congenital defects by visual examination

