 - must use 2 acceptable methods of birth control* if sexually active from Screening through 3 months after the last dose of study drug.
13. Sexually active male subject and his female partner who is of childbearing potential must use 2 acceptable methods of birth control* from Screening through 3 months after the last dose of study drug.

*Two acceptable methods of birth control are as follows:

- Condom (barrier method of contraception);
AND
- One of the following is required:
 - Placement of an intrauterine device (IUD) or intrauterine system (IUS) by the female subject or female partner of a male subject;
 - Additional barrier method: contraceptive sponge or occlusive cap (diaphragm or cervical/vault caps) with spermicidal foam/gel/film/cream/suppository by the female subject or female partner of a male subject.
 - For male subject or male partner of female subject, vasectomy or other procedure resulting in infertility (e.g., bilateral orchietomy) performed at least 6 months before Screening.
 - Tubal ligation in the female partner of a male subject performed at least 6 months before Screening.
 - Established and ongoing use of oral, injected, or implanted hormonal contraceptive by female partner of a male subject.

14. Female subject must not be breastfeeding at Screening or during the study period and for 3 months after final study drug administration.
15. Subject must agree not to donate sperm or ova from first dose of study drug through 3 months after the last dose of study drug.
16. Throughout the study, male subject must use a condom if having sex with a pregnant woman.
17. Subject must be able to swallow study drug and comply with study requirements.
18. Subject agrees not to participate in another interventional study while on treatment.

Waivers to the inclusion criteria will **NOT** be allowed.

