5.3 Efficacy and Pharmacodynamics Assessments

5.3.1 Efficacy Assessment

5.3.1.1 Survival Status and Subsequent Therapies

Subjects who are alive after the completion of the 30-day Follow-up Visit will continue to be contacted by site personnel for long-term survival follow-up every 30 days. This assessment may be conducted by telephone if the subject is unable to travel. Information on survival status and subsequent therapies will be obtained. Follow-up will continue for up to 2 years after the 30-day Follow-up Visit or until the final analysis.

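### The pregnancy-reporting trigger stops at treatment, while the protocol's own reproductive precautions run 3 months past the last dose

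*Protocol*

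**What the plan says.** **Reporting trigger.** Section 5.5.8 states: "If a female subject or partner of a male subject becomes pregnant during treatment, this should be reported as if it was an SAE". For how to report, the same sentence says "refer to Section 5.5.8 Procedure in Case of Pregnancy", which is a reference to itself. Later sentences cover consent of a pregnant partner, follow-up ("The Investigator will follow the medical status of the mother, as well as the fetus, as if the pregnancy is an SAE") and outcomes that meet SAE criteria. Those later sentences state no time limit relative to dosing.

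**Precaution window.** Where a female subject could conceive, Section 3.2 says she "must use 2 acceptable methods of birth control* if sexually active from Screening through 3 months after the last dose of study drug". For sexually active men whose partner could conceive, it says both "must use 2 acceptable methods of birth control* from Screening through 3 months after the last dose of study drug". Criterion 14 applies the same period to breastfeeding ("Female subject must not be breastfeeding at Screening or during the study period and for 3 months after final study drug administration"), and criterion 15 applies it to sperm and ova donation.

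**SAE window.** Section 5.5.5 describes SAEs as events "which will be collected from signing of the ICF until 30 days after last study drug administration".

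**Contacts after treatment.** The last scheduled urine pregnancy test is at the end-of-treatment visit, within 7 days of the last dose (Table 1). For subjects alive after the 30-day visit, Section 5.3.1.1 says they "will continue to be contacted by site personnel for long-term survival follow-up every 30 days". This lasts at most 2 years and stops earlier if the final analysis comes first. These contacts collect survival status and subsequent therapies. Appendix 12.9 keeps criteria 12 to 16 and refers to Section 5.5 for safety, but its schedule ends at the 30-day follow-up. Subjects who do not enter the open-label period also leave the study after their 30-day visit.

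The SAP contains no pregnancy-reporting rule.

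**The concern.** The protocol uses two different windows for one risk. Its precautions assume that exposure may matter for conception until 3 months after dosing stops, yet its reporting rule is triggered only by a pregnancy that begins on treatment. A site following 5.5.8 word for word would have no stated duty to report a pregnancy conceived two weeks after the last dose, whether in a subject or in a male subject's partner.

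At stake is a small number of rare safety observations that cannot be recovered later. Whether they reach the sponsor would depend on how each site reads the section. The open-label period has the same gap, and there every subject receives active drug.

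**Working it through.** There is no plan figure to reproduce. The check sets the windows side by side and adds simple arithmetic.

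**1. Does another rule close the gap?**

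| Provision | Does it make a post-dose conception reportable? |
|---|---|
| 5.5.8, first sentence | No. Limited to pregnancies that begin on treatment. |
| 5.5.8, follow-up and outcome sentences | Unclear. No time limit of their own, but they can be read as depending on the first sentence. |
| 5.5.2, SAE definition | No. Pregnancy is not a criterion; congenital anomaly is. |
| 5.5.5, SAE collection | No. Ends 30 days after the last dose and concerns SAEs. |
| 5.5.6, new-SAE sentence | No. Untimed, but about SAEs in a subject; a partner is not a subject. |
| 5.3.1.1, long-term contacts | No. Survival and subsequent therapies only. |

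A pregnancy conceived on treatment and detected later is already reportable, because the trigger is when the pregnancy begins. The gap concerns conception after the last dose.

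**2. Length of the gap.** Assumption: 3 months is 84 to 92 days.

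- Literal reading: the post-dose reporting window is 0 days, so 84 − 0 = 84 to 92 − 0 = 92 days are uncovered.
- Generous reading, in which treating the pregnancy like an SAE imports the 30-day window and conception within those 30 days counts: 84 − 30 = 54 to 92 − 30 = 62 days are uncovered. As a share, 54/84 = 64% to 62/92 = 67%.

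**3. Residual exposure.** Input: mean terminal half-life of 5.8 days in prostate cancer patients (Section 1.2.2.1). Assumptions: single-exponential decline, parent drug only. Fraction remaining at day t = 0.5^(t/5.8).

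| Days after last dose | Fraction of parent drug remaining |
|---|---|
| 7 | 0.5^(7/5.8) = 43% |
| 14 | 0.5^(14/5.8) = 19% |
| 30 | 0.5^(30/5.8) = 2.8% |
| 90 | 0.5^(90/5.8) = about 0.002% |

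The active metabolite is not in these figures. Section 1.2.2.1 gives its steady-state level as similar to the parent's, and the documents give no half-life for it. Parent exposure after the last dose is therefore real but concentrated in the first weeks.

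**The case against.** The strongest reply is that the section works better in practice than its first sentence suggests. Its later sentences carry no time limit, it asks for reporting in the manner of an SAE, and the section just above it (5.5.7) names Section 5.5.5. A careful site could import the 30-day window, which would cover the weeks when most parent drug remains. This stands as a limit on size: the uncovered period is a range, not a single figure. It does not close the gap, because more than half of the 3-month window stays open even then.

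Three stronger inferences are tempting, and the documents do not support them.

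- *That outcomes of such pregnancies would be lost.* Some would not be. A complication in a female subject that is itself an SAE within 30 days would be collected under 5.5.5. The untimed sentences in 5.5.6 and 5.5.8 may bring in others. Partners of male subjects are the least well covered.
- *That the animal findings show fetal harm.* Section 1.2.1.3 reports reproductive-organ and hormone-sensitive tissue changes in dosed rats and dogs. The reproductive-organ changes reversed or partially resolved after 8 weeks, and genotoxicity tests were negative. It describes no embryo-fetal toxicity. The case rests on the protocol's own 3-month window.
- *That a question at contacts already planned would solve it.* For open-label subjects and those who decline that period, no contact is scheduled after the 30-day visit.

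The practical effect is also small. Enrollment is complete at 165, the disease is advanced (assumed placebo median survival 7.0 months), and two contraceptive methods are required. The circular cross-reference is clerical.

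**Conclusion.** The inconsistency is real and modest. The protocol defines a reproductive-risk window of 3 months after the last dose but places no clear duty on sites to report a pregnancy conceived in it. The uncovered period is 84 to 92 days on the literal reading and 54 to 62 days if the 30-day SAE window is imported. The range rests on taking 3 months as 84 to 92 days and on which reading a site adopts; the text does not settle that. The half-life figures are supporting context only, limited to parent drug under a single-exponential assumption.

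This is a safety-reporting gap worth closing because closing it is cheap. It does not affect the overall survival analysis or any other efficacy result.

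**What to change.** - In Section 5.5.8, extend the reporting trigger so that it covers a pregnancy beginning on treatment or in the 3 months following the final dose, for subjects and for partners of male subjects. This matches inclusion criteria 12 to 15 and carries into Appendix 12.9 through its reference to Section 5.5.
- As an editorial correction, point the cross-reference in that sentence to Section 5.5.5.
- At the 30-day visit, instruct open-label subjects and those who decline the open-label period to notify the site of a later pregnancy, their own or a partner's.
- Ask about pregnancy at long-term contacts only where these still take place.

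Cost: one amended sentence, one reference, and one instruction at an existing visit; no new test or visit. Downside: after day 30, capture depends largely on subjects reporting for themselves, and sites and sponsor take on a small extra reporting burden.

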5.5.9 Emergency Procedures and Management of Overdose

If an overdose of enzalutamide occurs, the Medical Monitor must be contacted. An overdose is defined as any dose greater than the protocol-specified dose of enzalutamide 160 mg once daily. In the event of an overdose, stop treatment with study drug and initiate general supportive measures taking into consideration the enzalutamide $t_{1/2}$ of 5.8 days.

Neither the effects of overdose of enzalutamide nor an antidote to overdose are known. Subjects may be at increased risk of seizures following an overdose of enzalutamide.

All overdose events are to be reported within 24 hours of awareness by the study site per Section 5.5.2, whether or not the event meets AE criteria.

5.5.10 Supply of New Information Affecting the Conduct of the Clinical Study

When new information becomes available necessary for conducting the clinical study properly, the Sponsor will inform all Investigators involved in the clinical study as well as the regulatory authorities. Investigators should inform the IRB/IEC of such information when needed.

The Investigator will also inform the subjects, who will be required to sign an updated ICF in order to continue in the clinical study.

5.6 Test Drug Concentration

5.6.1 Pharmacokinetic Assessments

Plasma samples will be analyzed to determine enzalutamide and N-desmethyl enzalutamide concentrations in all subjects treated in the study. In addition, inactive metabolite (M1) of enzalutamide may be analyzed. Pharmacokinetic samples will be obtained before study drug dosing. Blood samples will be collected from a vein or port that is not used for drug infusions. Blood sampling, processing, storage and shipment instructions are provided in a lab manual. Samples will be shipped to and analyzed by a Sponsor designated analytical laboratory.

5.7 Other Measurements, Assessments or Methods

5.7.1 Blood Sample for Future Pharmacogenomics (PGx) Analysis (Retrospective PGx Analysis)

A PGx research may be conducted in the future to analyze or determine genes of relevance to clinical response, pharmacokinetics and toxicity/safety issues. After randomization (see schedule of assessments), approximately 5 mL sample of whole blood for possible retrospective PGx analysis will be collected using a vacutainer tube containing ethylenediaminetetraacetic acid. After collection, gently invert the blood sample 8 to 10 times. The blood collection tube may either be stored upright at 4°C for up to 5 days prior to shipment or stored frozen at -20°C or below at the site for extended storage. Samples will be shipped to a Sponsor designated banking contract research organization (CRO).

Labels should uniquely identify each sample and contain at least:

- Protocol number (9785-CL-3021),
- Subject number, and
- Purpose and biological matrix (i.e., “biobanking”, “whole blood”).

Details on sample collection, labeling, storage and shipment procedures will be provided in a separate laboratory manual.

See Appendix [12.3](#) Retrospective PGx Sub-study for further details on the banking procedures.

